**Description of Study Intervention:**

Up to 30 patients will be equally randomized to receive once daily either 10 mg dose of GSK2256294 or placebo enterally for a duration of 10 days.

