## 4.2 SCIENTIFIC RATIONALE FOR STUDY DESIGN

This is a safety and proof of concept study. A randomized trial is needed to determine the effect of GSK2256294 on EETs metabolism, because EETs levels vary over the natural course of recover after SAH, and a placebo group is needed for comparison. Randomization and double blinding additionally limit the influence of potential confounders and selection bias.

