## 6.3 MEASURES TO MINIMIZE BIAS: RANDOMIZATION AND BLINDING

Participants who meet all eligibility criteria and consented for study participation will be randomized by notifying the research pharmacy service. A randomization list will be generated by computer generated sequence and will determine whether the subject receives active drug or matched placebo. The randomization procedure will require confirmation of the eligibility criteria to ensure that the integrity of the randomization is maintained. Subjects will be randomized to one of the two treatment arms based on an unrestricted or "fair-coin" randomization procedure.

Randomization will be carried out in STATA using a uniform distribution with a specific random number seed so that the results are reproducible. The research pharmacy service will maintain the randomization list and provide the study drug as appropriate. All participants who complete the informed consent process will be assigned a study identification number. Numbers will be assigned in consecutive order starting with the number 100. This number will be followed with another two-digit number representing the randomization sequence starting at 01. Participants will be referenced by the study identification number.

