### 8.2 BASELINE EVALUATION

Baseline subject evaluation and testing will be performed in conjunction with routine intensive care unit treatment and monitoring. Data will be collected from the medical record or patient/surrogate interview.

- **Patient Demographics:** Ethnographic characteristics (age, sex, race/ethnicity, weight, height, BMI), level of education, and detailed contact information for follow-up

- **Characteristics of present illness:** Hunt and Hess Score, Fisher grade, location of aneurysm, surgical vs interventional treatment (completed or planned) and Glasgow Coma Scale (GCS) will be collected at the time of randomization.
- **Baseline Physiologic Data:** The first laboratory results and vital signs obtained at the time of ICU admission will be recorded, and detailed in the variable list in section 12. We will also collect details about history of preexisting medical comorbidities using the Charlson Comorbidity Index Score, screening for tobacco use, and targeted questions about neurologic history. A baseline EKG will be performed as part of the standard of care, and reviewed for evidence of conduction abnormalities or acute myocardial ischemia.
- **Admission medications:** Selected classes of medications administered from the time of ICU admission to randomization will be recorded. We will also record selected classes of home medications the patient may have been taking prior to hospitalization.

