## 9.2 SAMPLE SIZE DETERMINATION

The total sample size was selected *a priori* based on the need to evaluate and describe the safety profile of the study drug in this patient population.

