#### 9.4.3 ANALYSIS OF THE PRIMARY ENDPOINT

Safety will be assessed by clinical review of all relevant parameters including vital signs, laboratory values, adverse events, serious adverse events, disease related events, and mortality. Unless specified otherwise, the safety analyses will be conducted for the safety population.

Summary tables and listings will be provided for all reported adverse events, defined as adverse events that start on or after the first administration of study drug. The reported adverse event term will be assigned a standardized preferred term.

Adverse events will be summarized based on the number and percentage of patients experiencing the event. In the event a patient experiences repeat episodes of the same adverse event, then the event with the highest severity grade and strongest causal relationship to study treatment will be used for purposes of incidence tabulations. Tabular summaries will be provided for all adverse events, the relationship to study drug treatment the maximum severity grade, action taken, and whether the event qualified as SAE or not.

Daily safety laboratory test results will be summarized in a descriptive manner by calculating the mean, standard deviation, median, and range. Directional shifts (comparing baseline grade with worst post-baseline grade) will be analyzed using standard shift tables. The shift table will present directional shifts from baseline to above or below the laboratory standard normal range using the maximum increase and/or decrease observed throughout the course of treatment/observation.

Vital signs will be summarized in a descriptive manner by calculating the mean, standard deviation, median, and range in the same manner described for laboratory values.

All deaths will be reported in a patient listing, which will include the primary cause of death and the number of days between the date of the last dose of study drug and death.

---

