#### 9.4.4 ANALYSIS OF THE SECONDARY AND TERTIARY ENDPOINTS

Secondary endpoints will be compared between the study drug and placebo groups using the per-protocol population. Serum and CSF EET/DHET ratios and biomarkers will be presented as

the mean and standard deviation, and differences evaluated with two sample Student's t-test with a two-sided type 1 error rate of 0.05%.

Tertiary endpoints will be compared descriptively between the groups based on the mean, median, standard deviation and range.

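### Bleed-severity grades are collected at randomisation but enter no planned safety or clinical-outcome comparison, so a chance severity imbalance could be mistaken for a drug effect.

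*Combined protocol and SAP*

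**What the plan says.** **Severity is recorded.** Section 8.2 lists "Hunt and Hess Score, Fisher grade, location of aneurysm" among the characteristics of the present illness, and says these "will be collected at the time of randomization". The supplied text does not mention either grade again.

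**Allocation does not balance it.** The synopsis says "Up to 30 patients will be equally randomized to receive once daily". Section 6.3 says "Subjects will be randomized to one of the two treatment arms based on an unrestricted" (fair-coin) procedure, with no blocks and no strata. Section 4.2 relies on the design for protection: "Randomization and double blinding additionally limit the influence of potential confounders and selection bias".

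**The comparisons do not use it.** Section 3 intends AEs and SAEs to be compared between drug and placebo, with specific screening for complications such as seizure, cardiomyopathy, infection and ventilation. Section 9.4.3 then plans clinical review, tables and listings: "Adverse events will be summarized based on the number and percentage of patients experiencing the event". For clinical outcomes, section 9.4.4 says "Tertiary endpoints will be compared descriptively between the groups". Neither section names a covariate or a stratum.

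**Two statements soften this.** Section 9.4.1 promises a descriptive table of baseline characteristics but does not list its variables. Section 3, where it explains the biomarker time points, leaves the investigators free to adjust for marked baseline differences when interpreting results.

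**The concern.** Section 8.6.5 itself treats most of the screened complications, and disease-related death, as expected in this population. They are consequences of the bleed, and their frequency plausibly rises with its severity. If one arm happens to receive more severe bleeds, its event counts will tend to be higher whatever the drug does. The same holds in the other direction, where a real harm could be masked.

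Safety is to be judged by reading counts without intervals or tests, so nothing in the planned output separates a grade effect from a drug effect.

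The tertiary objective raises a second issue. Its estimates are meant to help size a larger trial. Pooled DCI, mRS and GOSE figures that are not broken down by grade carry over poorly to a trial with a different case mix, even if the arms here happen to balance.

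**Working it through.** The protocol has no power, precision or sample-size figure to reproduce. Section 9.2 says only "The total sample size was selected *a priori* based on the need to evaluate and describe the safety profile".

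**Inputs from the protocol:** N up to 30; two arms; fair-coin allocation.

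**Assumptions, because the protocol gives no figures:** poor-grade share 30% (range 20% to 50%); event risk 60% in poor and 15% in good grade, with 50% and 25% as a weaker contrast. Other values are marked where used.

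**1. How likely is an imbalance?**

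- *Arms of exactly 15.* The difference of two independent Binomial(15, p) counts gives:

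| Poor-grade share | Differ by 3 or more patients | Differ by 4 or more patients |
|---|---|---|
| 20% | 25% | 11% |
| 30% | 32% | 16% |
| 40% | 35% | 19% |

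- *Fair-coin arm sizes, as planned.* A 15:15 split has probability C(30,15)/2^30 = 14%, and a split of 11:19 or worse has probability 20%. Weighting the hypergeometric count of poor-grade patients by the probability of each arm size, the chance that the share differs by 20 points or more is 18%, 27%, 29% and 36% for overall shares of 20%, 30%, 40% and 50%.

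**2. How far does an imbalance move the crude result?**

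Spurious risk difference = (risk in poor grade − risk in good grade) × difference in poor-grade share.

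For a 4-patient imbalance with 15 per arm, the difference in share is 4/15 = 0.267:

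- 60% v 15%: 0.45 × 0.267 = 0.12, or 12 points.
- 50% v 25%: 0.25 × 0.267 = 0.067, or 7 points.

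In patients, take 8 v 4 poor-grade and risks of 60% and 20%. The expected numbers with an event are 8 × 0.60 + 7 × 0.20 = 6.2 and 4 × 0.60 + 11 × 0.20 = 4.6. With an inert drug, the chance of at least 3 extra patients with an event in the worse arm rises from 14–15% (6 v 6 poor-grade) to 32–36% (8 v 4). These ranges cover risks of 50% v 15% and 60% v 20%.

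**3. How does that compare with ordinary noise?**

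SE of a risk difference = √(2q(1−q)/15). For q = 0.3 this is 16.7 points and for q = 0.5 it is 18.3 points. The shift in step 2 is therefore less than one standard error.

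**4. What does stratifying by grade achieve?**

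Simulated trials with an inert drug, N = 30, fair coin and 30% poor grade, crude v Mantel-Haenszel stratified:

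| | 60% v 15% | 50% v 25% |
|---|---|---|
| Poor-grade share at least 20 points higher in one arm: mean risk difference | 13 points crude, about 0 stratified | 7 points crude, about 0 stratified |
| Same trials: false difference of 20 points or more against that arm | about 32% v 10% | about 23% v 13% |
| All trials: SD of the risk difference | 16.8 v 15.2 points | 17.4 v 17.2 points |
| All trials: false difference of 20 points or more, either direction | 24% v 19% | 26% v 25% |

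Stratifying removes the shift in trials where grade is unbalanced. Averaged over all trials the gain is modest, or close to nil if grade predicts the event only weakly. In about 56% of simulated trials, at least one arm had three or fewer poor-grade patients, so stratified intervals for individual event types would rest on almost no data.

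**The case against.** The strongest opposing case has four parts.

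- **An imbalance would be seen.** Section 8.2 places the grades in the baseline evaluation, and 9.4.1 promises a baseline table. On a natural reading, a reader would find them there. This stands in part: 9.4.1 does not name the variables, and a baseline table shows an imbalance without showing what it did to event rates.
- **Safety does not rest on counts alone.** Section 9.4.3 includes clinical review, event listings and a death listing with primary cause, and 8.6.3.2 requires a causality judgement for every AE. A reviewer can weigh severity case by case. This stands, and it is why misreading is a risk and not a certainty. It does not put grade into any comparison.
- **Nothing inferential is at stake.** No test is planned for safety or clinical outcomes, section 3 says the trial is not powered for the latter, and randomisation makes the crude difference unbiased on average. All true. The low false-rejection rate of Fisher's exact test with 8 v 4 poor-grade patients (about 2.5%) offers no protection, however, because no such test is planned.
- **Adjustment buys little at this size.** Most spurious differences come from small numbers, not grade. This stands, and it limits the remedy.

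The permission in section 3 to adjust for baseline differences is no answer: it is optional, names no variable or method, and sits in the biomarker rationale.

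**Conclusion.** The point holds in a limited form. Grade is collected and enters no planned safety or clinical-outcome comparison, and allocation leaves its balance to chance. A difference of 20 points or more in poor-grade share has a probability of roughly one in six to one in three, and in such trials it moves the crude risk difference by about 7 to 13 points with an inert drug. These sizes rest on the assumed grade mix and event risks. The protocol supplies neither.

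A reader might infer that an imbalance will be read as drug harm or benefit. The documents do not support that. The baseline table may reveal it, clinical review and per-event causality assessment work against it, and the shift is smaller than the 17 to 18 point standard error. A reader might also infer that the crude comparison is biased by design. It is not: this is chance imbalance in a small trial, for which a recorded baseline value is available but unused. Nor do the numbers support adjusted estimates for every event type.

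**What to change.** Add to sections 9.4.1, 9.4.3 and 9.4.4, before unblinding:

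1. Hunt and Hess and Fisher grade are shown by arm in the baseline table and for each patient in the SAE and death listings.
2. Mortality, any SAE, any disease-related event, DCI, mRS at discharge and 90 days, and GOSE at 90 days are tabulated by arm within Hunt and Hess I–III and IV–V. These tables also serve as the planning estimates for the next trial.
3. For the four composite or key binary outcomes only (any SAE, any disease-related event, mortality, DCI), a severity-stratified risk difference with 95% CI, such as Mantel-Haenszel, is reported beside the crude one and labelled as a sensitivity analysis. It is not produced for each event type.

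The crude figures stay primary.

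The cost is a few sentences and a few tables from data already collected, with no change to conduct. The drawbacks are sparse strata, wide intervals and a modest precision gain. The attached schedule of activities and the variable list were not available; if either already fixes the content of the baseline table, the first item may need only a cross-reference.

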## 3 OBJECTIVES AND ENDPOINTS

- **Primary Objective:** Determine the safety of administration of GSK2256294 in patients with aneurysmal SAH.

Frequencies of AEs and SAEs: We will compare AEs and SAEs between the drug and placebo groups. We will also compare daily safety labs (serum sodium, blood glucose, blood urea nitrogen (BUN), creatinine, hematocrit, peripheral white blood cell count) between the groups. Specific to this patient population, we will also specifically screen for disease related events including seizure, new onset cardiomyopathy, NSTEMI/STEMI, hyponatremia, hospital acquired infection, mechanical ventilation, and thromboembolic events. We will describe the severity of headache (on a daily scale of 0-10).

**Justification:** Prior phase 1 studies of GSK2256294 have been in healthy volunteers with limited physiologic monitoring. The most common adverse event was headache. We will assess safety in this critically ill patient population with special focus on common sequelae of subarachnoid hemorrhage.

- **Secondary Objective:** Determine the pharmacodynamic effects of administration of GSK2256294 in patients with aneurysmal SAH.

To evaluate the effect of enzymatic inhibition on circulating EETs levels, we will measure day 7 and day 10 serum EET/DHET ratios. EETs levels will be measured using liquid chromatography and mass spectroscopy.

To evaluate the possible effect of enzymatic inhibition on CSF EETs levels we will measure day 7 and day 10 CSF EET/DHET ratios, and compare the drug and placebo groups. We will also measure other lipid metabolic substrates of sEH at days 7 and day 10, specifically serum epoxyoctadecenoic acid (EPOME) and dihydroxyoctadec-12-enoic acid (DPOME), to assess sEH enzyme activity.

To evaluate more downstream effects on measures of endothelial injury and neuroinflammation, we will measure multiple biomarkers in the blood and CSF at day 7 and day 10 (Table 1). The biomarkers chosen are surrogate endpoints representing pathways of the inflammatory cascade associated with clinical endpoints in SAH.

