## 4 STUDY DESIGN

### 4.1 OVERALL DESIGN

The study is a single site double-blind, placebo-controlled, phase 1b randomized trial to evaluate the safety and preliminary pharmacologic activity of GSK2256294 in patients with

aneurysmal SAH. We hypothesize that inhibition of the sEH enzyme will be safe in patients with SAH, and result in increased EETs availability at the neuroendothelium, eventually leading to reduced neuroinflammation. Up to 30 patients will be equally randomized to receive once daily enteral administration of either 10 mg dose of GSK2256294 or placebo for a duration of 10 days.

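### The continuous daily lab summaries behind the between-group safety comparison use raw values only, so entry differences between small arms may blur the reading

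*Combined protocol and SAP*

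**What the plan says.** Section 3 (Objectives and Endpoints) places a by-group comparison of six labs (sodium, glucose, BUN, creatinine, hematocrit, white cell count) under the primary objective: "We will also compare daily safety labs". It names no estimator or test.

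Section 9.4.3 sets out how safety is judged: "Safety will be assessed by clinical review of all relevant parameters including vital signs, laboratory values, adverse events, serious adverse events, disease related events, and" (the list closes with deaths). For the labs it says: "Daily safety laboratory test results will be summarized in a descriptive manner by calculating the mean, standard deviation, median, and range". The next sentence brings in baseline: "Directional shifts (comparing baseline grade with worst post-baseline grade) will be analyzed using standard shift tables". Those tables show movement from baseline to outside the normal range, using the largest rise or fall over the whole course. Vital signs get the same four statistics, in the manner used for labs. Whether that includes the shift tables is not stated.

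On baseline, Section 8.2 says: "The first laboratory results and vital signs obtained at the time of ICU admission will be recorded". Section 9.4.1 tabulates baseline characteristics for all participants.

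On size and allocation, Section 4.1 says "Up to 30 patients will be equally randomized to receive once daily enteral administration of either 10 mg dose of GSK2256294 or placebo", and Section 6.3 says "Subjects will be randomized to one of the two treatment arms based on an unrestricted or 'fair-coin' randomization procedure". Section 9.2 gives the reason for the sample size: "The total sample size was selected *a priori* based on the need to evaluate and describe the safety profile of the study drug". It states no effect size, SD or power.

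**The concern.** The objective promises a comparison between groups, but the continuous part of the analysis section offers only raw daily summaries. It contains no change from baseline, no between-arm difference, no baseline adjustment and no daily count of patients.

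The shift tables use each patient's own baseline but answer a different question. A creatinine that rises clearly yet stays within the normal range records no shift. A patient already above the range at entry cannot newly cross the upper limit. Because the tables take the extreme over the whole course, they give no day-specific contrast between arms.

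What is at stake is how readable the safety tables are. A clinical reviewer looking at mean creatinine by arm on day 7 cannot tell from that table how much of a gap was there at entry. Nor can the reviewer tell whether the patients measured on day 7 are those measured on day 1. Section 7.1 allows treatment to end early through a related SAE, death, discharge or withdrawal, and Section 8.4.1 ties the daily assessments to days on which study drug is received. An entry difference could be taken for a drug signal, or could hide one.

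**Working it through.** The plan has no figure to reproduce, since no power, SD, correlation or margin is given for labs or vital signs. Everything below is in SD units of a single lab. The only inputs from the documents are a total of up to 30 patients (Section 4.1) and unrestricted allocation (Section 6.3). The correlation ρ between baseline and follow-up is an assumption, shown over 0.3 to 0.8.

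**1. Chance difference at entry.** The standard error of the difference in baseline means is √(1/n₁ + 1/n₂). By the normal approximation, P(|difference| > 0.5 SD) = 2 × [1 − Φ(0.5/SE)].

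| Split | SE (SD) | P(difference > 0.5 SD) |
|---|---|---|
| 15/15 | √(2/15) = 0.365 | 0.171 |
| 12/18 | 0.373 | 0.180 |
| 10/20 | 0.387 | 0.197 |

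Under a fair coin with 30 patients, the chance that the smaller arm has 10 or fewer is about 0.10. Averaging over the Binomial(30, 0.5) arm sizes gives 0.179. The result is about 17–18% per lab.

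**2. How much of an entry difference persists.** With equal SDs at both times and a linear relation, an entry difference of 0.5 SD leaves an expected ρ × 0.5 SD in the raw follow-up difference even with no drug effect:
- 0.15 SD at ρ = 0.3
- 0.25 SD at ρ = 0.5
- 0.35 SD at ρ = 0.7

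**3. Effect of using baseline on precision.** At 15 per arm and relative to the raw comparison, the variance is multiplied by 2(1 − ρ) for change scores and by 1 − ρ² for ANCOVA.

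| ρ (assumed) | SE raw | SE change score | SE ANCOVA | ANCOVA variance ratio |
|---|---|---|---|---|
| 0.3 | 0.365 | 0.432 | 0.348 | 0.91 |
| 0.5 | 0.365 | 0.365 | 0.316 | 0.75 |
| 0.7 | 0.365 | 0.283 | 0.261 | 0.51 |
| 0.8 | 0.365 | 0.231 | 0.219 | 0.36 |

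At ρ = 0.5 the variance falls by 1 − 0.75 = 25%. If a 95% interval were reported, its half-width would go from 0.748 SD (t on 28 df) to 0.649 SD (t on 27 df). The change score is worse than the raw value at ρ = 0.3 and only equal at ρ = 0.5. Change from baseline is therefore a useful display, but ANCOVA is the better between-arm estimate.

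**4. What changes in the plan.** The only hypothesis test in Section 9 is the t-test on the secondary biomarkers (Section 9.4.4). No planned test, interval or decision on labs or vital signs depends on the figures above.

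**The case against.** The strongest reply is that the plan is coherent for a small descriptive safety study. Safety is judged by clinical review, the sample size was chosen to describe safety, and raw summaries stand beside shift tables and a baseline table. Under randomization the raw difference is unbiased, and chance imbalance is already part of its standard error. This largely stands, and it limits the point to an improvement.

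A reader might infer that baseline is ignored for labs altogether. The documents do not support that, because Section 9.4.3 plans shift tables from each patient's own baseline. For vital signs the text is unclear, which is not the same as baseline being left out.

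A reader might also infer that chance differences will be read as drug effects, or that the trial loses power. Neither follows. Reviewers will have the shift and baseline tables, so misreading is a risk and not a certainty. No test on these labs is planned, so there is no planned power to lose.

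The objection also bears on the remedy. Section 8.2 records the first values at ICU admission, and Section 8.1 allows enrollment up to 48 hours later. The documents do not establish that a last pre-dose value is recorded for every lab and vital sign, and the detailed variable list is not in the text. Baseline must be defined to fit what is collected.

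The changing set of patients is partly covered: Section 7.1 continues study procedures after treatment ends, Section 9.4.1 summarises discontinuations, and Section 9.4.2 examines missing-data patterns. Even so, none of these puts the daily count in the lab tables, and ANCOVA at day 7 or 10 still includes only those measured then.

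**Conclusion.** The point holds as a modest one. Section 3 promises a between-group comparison of the daily labs, and the continuous summaries in Section 9.4.3 support it only with raw values. The shift tables do not fill that gap, because they miss change within the normal range and give no contrast by day.

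The size that rests on the documents alone is the chance of an entry difference above 0.5 SD: about 17–18% per lab if all 30 patients are enrolled, using the normal approximation. The carry-over and precision figures also need an assumed correlation and are illustrative. The 25% variance reduction belongs to ρ = 0.5, and the range over ρ = 0.3 to 0.8 is 9% to 64%. The consequence is a safety comparison that is harder to interpret than it need be. No planned conclusion is invalidated.

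**What to change.** In Section 9.4.3, keep the raw summaries and the shift tables, and add:

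- **Baseline definition.** The recorded ICU-admission value, or the latest value recorded before the first dose where one is available.
- **Daily tables.** For each daily lab and vital sign, by-arm change from baseline and the number of patients contributing on each day.
- **Between-arm comparison.** At days 7 and 10, a baseline-adjusted (ANCOVA) difference with a 95% interval, in preference to a difference in change scores.
- **Status.** A statement that these are descriptive, with no multiplicity claim.
- **Vital signs.** A sentence saying that they are handled in the same way as labs.

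The cost is a few lines of standard STATA code and more descriptive tables. The baseline covariate uses one degree of freedom in each ANCOVA. No new data are needed where the admission value serves as baseline.

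One side effect should be accepted openly. Intervals across six labs plus vital signs at two days will produce some that exclude zero by chance, which is why the descriptive label matters.
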